Essure HyCoSy Ultrasound Grant Application

Can Contrast Infused Sonography Using Air Bubbles Replace Hysterosalpingogram as the Diagnostic Evaluation of Fallopian Tube Patency Following Hysteroscopic Sterilization Using Essure™?

Revision 2; Version date: 04/19/2016

[name] M.D., MMM [name], and [name]

NCT02628873

Hypothesis:

We hypothesize that performing saline infused sonography (SIS) with directed air bubbles for hysterosalpingo-contrast sonography (HyCoSy) is at least as equivalent or superior in evaluation of fallopian tube patency following hysteroscopic Essure™ tubal sterilization in those undergoing X-ray hysterosalpingography (HSG). We also hypothesize that performing HyCoSy with air bubbles is more cost-effective and less painful than HSG.

Objectives:

Currently, in the USA, Essure is approved by the Food and Drug Administration (FDA) for hysteroscopic sterilization (1). The effectiveness of permanent sterilization is 99.8%, with successful bilateral placement rate for each delivery system approximately 96.5% (1,2). Current FDA labeling for Essure requires an HSG 3 months after placement to confirm the proper coil position and tubal occlusion (1). However, HSG is not the ideal confirmatory test given the following inherent issues (3-5):

1. Exposure to ionizing radiation
2. Cost
3. Patient discomfort
4. Inconvenience
5. Poor inter-observer reproducibility
6. Variability in the technique
7. Tubal spasm potentially creating the false impression of proximal tubal occlusion

In fact, 30% of unintended pregnancies after hysteroscopic tubal occlusion placement have been attributed to misinterpretation of the HSG (6). Thus, our primary objective is to determine if HyCoSy with air bubbles is equivalent to HSG in the diagnosis of tubal patency in patients undergoing hysteroscopic sterilization using Essure™. Secondary objectives include 1) Pain assessment of each

procedure and 2) Cost analysis. To address these objectives we propose the following specific aims:

Primary Specific Aims:

1. To demonstrate an equivalent or superior evaluation of fallopian patency by HyCoSy using air-bubbles in comparison to HSG.

Secondary Specific Aims:

1. To compare pain scores in those undergoing SIS/HyCoSy to HSG in order to assess overall tolerability of SIS/HyCoSy.
2. To compare assessment of the uterine cavity using SIS air-bubble contrast using SIS-catheter in comparison to HSG.

Background and Significance:

Tubal disease accounts for 30 to 40% of all cases of infertility (7,8). The gold standard for tubal evaluation is laparoscopy with dye (chromopertubation). The standard non-operative method for evaluating pelvic anatomy has been the HSG (9-11). The HSG, however, requires exposure to ionizing radiation and the need for iodinated contrast material. Proper technique in performing an HSG is imperative since inadequate uterine distension may result in poor visualization or overzealous instillation may easily obscure uterine pathology or cause inadvertent tubal spasm suggesting pathology (4, 7-11). In contrast, the use of sonography combined with intrauterine saline instillation, termed SIS, has become routine for evaluation of intrauterine cavity pathology and has been shown to have similar predictive value to hysteroscopy (12-15).

A number of clinical trials have suggested SIS application in fallopian tube assessment for infertility (16-48). Contrast agents that have been described include the use of a suspension of galactose micro-particle granules (Echovist-200®), perflutren lipid microspheres (Definity®), and air bubbles to enhance contrast in the fallopian tubes (sonosalpingography-SSG or hysterosalpingo-contrast sonography-HyCoSy). Each has been reported to have similar diagnostic accuracy as HSG with iodinated contrast material (17-21). Furthermore, there are added advantages of minimizing risks (i.e. no ionizing radiation), better 3-dimensional imaging of the uterus and allowing for the evaluation of tubal and ovarian pathology during the same study. Disadvantages of its use include false positive results of tubal occlusion related to tubal spasm, difficulty assessing fallopian tubes with abnormal anatomy and interference of echogenicity from over-lying bowel. Additionally, only one tube can be visualized at a time, therefore it is possible to miss flow through the contralateral tube with initial injection.

Specifically, studies using Echovist-200 (developed for cardiac ultrasound) demonstrated 83% agreement with HyCoSy compared to laparoscopy, compared to a 76% agreement with HSG and laparoscopy (22,42, 49-52). The contrast material, however, is very expensive (>\$500), obviating its routine use in the office setting. The use of perflutren lipid microspheres (Definity®) in cardiac imaging has allowed for stability of the contrast media (50-52). Recent studies using Definity® microspheres have been described for its use with HyCoSy to assess tubal occlusion after Essure Tubal Sterilization, which demonstrated 100% agreement with HSG in assessing tubal patency

and 82% agreement with respect to tubal occlusion. Moreover, patients preferred undergoing HyCoSy in the comfort of the gynecology office rather than the radiology department (50). As such, while Definity® appears to be a safe and effective contrast media for HyCoSy, however, this contrast is not FDA approved and further studies are needed to determine its diagnostic accuracy and reproducibility.

A substituted a mixture of saline and air for distending media has also been described (16, 40–43) where some vigorously shake a syringe of saline and air creating air bubbles immediately before infusion, while others have described filling a syringe with both air and saline and tilting the syringe with the intermittent infusion of air followed by saline in increments of 1–3 mL (38,39, 53-55). Positive and negative predictive values for air contrast HyCoSy appears to be similar to other contrast materials for both tubal patency and occlusion when compared to both laparoscopy and HSG (38,55). However, as air bubbles disappear quickly, tubal assessment is limited. This method has been shown to have excellent predictive value (80%–87%) when compared to laparoscopy.

Recently, an FDA approved device, Femvue™ Saline-Air Device, creates and delivers a consistent alternating pattern of saline and filtered air as a continuous stream in a controlled fashion allowing for fallopian tube evaluation under ultrasound guidance (56). Our objective is to determine if saline infused sonogram (SIS)-HyCoSy with Femvue™ Saline-Air Device is equivalent or superior to HSG in evaluation of fallopian tube occlusion in those undergoing HSG following Essure hysteroscopic tubal occlusion as Comparative studies to HSG, are lacking.

The advantages of HyCoSy revolve around its applicability in the office, its cost effectiveness and the avoidance of radiation exposure. Although shown to be a practical procedure with investigations yielding high accuracy results for both tubal patency and tubal occlusion, as mentioned previously, studies are still needed to evaluate this subject matter further. Minimal data exist directly comparing HSG versus HyCoSy with air bubble contrast media as the confirmatory test for post hysteroscopic tubal occlusion. We propose to determine the predictive value and possible overall superiority of HyCoSy to HSG from a time effective and pain scale model.

Experimental Design:

Thirty-six women who are undergoing post-Essure tubal occlusion evaluation will be invited to participate in this study. Subjects will be recruited and screened from the practice of Wright State OB-GYN Physicians.

Inclusion Criteria

1. Documentation of normal PAP smear within one year prior to subject enrollment in study.
2. Written consent to this study must be given voluntarily.
3. Need for evaluation of tubal status for post-Essure tubal occlusion.
4. Negative urine pregnancy test.

Exclusion Criteria

1. Any prior endometrial ablation procedures or plans to undergo endometrial ablation procedures prior to the Essure confirmation test.
2. History of unresolved dysfunctional uterine bleeding (DUB).
3. History of a hysterectomy.
4. Current urogenital disease.
5. History of allergic response to IVP dye (exclusion for HSG).
6. Abnormal pap smear.
7. Positive urine pregnancy test.

Procedure

As part of their post-Essure Tubal occlusion assessment, both air bubble HyCoSy and HSG will be performed at the same visit. Patients will undergo air bubble HyCoSy first, performed in the office setting, followed by HSG, which will be performed in the radiologic suite Miami Valley Hospital. A Likert Pain Scale will be completed prior to testing and at completion of the study for each procedure (See below).

1. Saline Infused Sonography (SIS):

SIS will be performed either during the follicular phase of a spontaneous menstrual cycle or following a progestin withdrawal bleed. All patients will be asked to take NSAIDs one hour prior to the procedure. A 2-mm lumen SIS balloon catheter will be placed transcervically during a speculum examination, with the balloon distended in the lower uterine segment or cervical canal. Routine transvaginal sonography of the endometrium, myometrium, and adnexae will be initially performed, followed by instillation of 5-10ml of sterile saline through the catheter for uterine evaluation. Transvaginal sonographic images of the sagittal and coronal views of the pelvis will be recorded with still images and video.

2. Hysterosalpingo-Contrast Sonography (Air Contrast HyCoSy):

This will be a randomized prospective trial, where patient will be randomly allocated initially to either the Air Contrast HyCoSy or the Hysterosalpingogram. At least one hour between procedures will be required.

Air-Contrast HyCoSy

After completion of the SIS evaluation of the uterine cavity, Air Contrast HyCoSy contrast will then be performed through the same catheter under direct ultrasound visualization. The FemVue™ Saline-Air Device will be used for the air contrast HyCoSy. It is an FDA approved diagnostic tool used with SIS to evaluate the intrauterine cavity. The device is applied to the SIS catheter so that when filled, is an alternating mixture of air and saline that will be infused into the uterine cavity acting as a contrast agent for HyCoSy.

If fallopian tube patency is indeterminate, the patient will be repositioned into a lateral position at approximately 45° in order to better visualize the fallopian tube as previously described (17). The SIS catheter will be removed at completion of the HyCoSy procedure. Each patient will complete a pain and comfort survey using a Likert Scale questionnaire prior to and following the SIS and HyCoSy procedure (See Below). After completion of this survey, the patient will be directed to the radiology suite for their HSG.

3. Hysterosalpingography (HSG):

This will be a randomized prospective clinical trial, where patients will be randomly allocated to the Air Contrast HyCoSy or HSG initially followed by the other test with at least 1 hour between procedures. The primary outcome of interest is the agreement between the HSG and air-bubble HyCoSy in evaluating tubal patency. For this purpose the HSG will indicate either tubal patency or non-patency and will be considered as the gold standard, and the air-bubble HyCoSy will indicate either patency, non-patency, or inconclusive and compared to the gold standard HSG. Agreement between the evaluations will be measured using the kappa (κ) statistic. To detect a difference in kappa (a correlation) as small as 95% vs 99% you will need 36 with a 20% non-compliance rate. This means that you will be able to detect a difference as small as 95-99 OR anything larger. This translates into the assumption that even a 95% kappa is acceptable enough to call the methods 'the same.'

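### Kappa against HSG as the truth cannot show superior patency evaluation, and with 29 to 36 women even perfect agreement cannot show kappa above 0.95

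*Combined protocol and SAP*

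**What the plan says.** The Hypothesis states that HyCoSy "is at least as equivalent or superior in evaluation of fallopian tube patency". Aim 1 under Primary Specific Aims reads "To demonstrate an equivalent or superior evaluation of fallopian patency by HyCoSy using air-bubbles in comparison to HSG". The objective at the end of the FemVue paragraph in Background and Significance asks whether HyCoSy "is equivalent or superior to HSG in evaluation of fallopian tube occlusion". The Objectives section is narrower: "our primary objective is to determine if HyCoSy with air bubbles is equivalent to HSG in the diagnosis of tubal patency".

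Statistics names agreement as the primary outcome, measured by kappa, and fixes the reference: "For this purpose the HSG will indicate either tubal patency or non-patency and will be considered as the gold standard". HSG has two outcomes. HyCoSy has three, because it may be inconclusive. The section then says that 36 are needed, allowing for 20% non-compliance, to detect kappa of 95% versus 99%, and that a 95% kappa is good enough to regard the methods as the same. It gives no alpha, power, sidedness, confidence bound, expected patency or unit (woman or tube). Experimental Design gives the number as women: "Thirty-six women who are undergoing post-Essure tubal occlusion evaluation will be invited to participate in this study".

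**The concern.** There are two separate problems.

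(a) Once HSG is the truth, every discordance counts against HyCoSy. If HyCoSy were right where HSG was wrong, it would be scored as an error. The Objectives section lists tubal spasm and misread HSGs among the weaknesses of HSG, so such cases are expected. An analysis that cannot go beyond identity with HSG cannot deliver the superior half of Aim 1.

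(b) The only criterion for calling the methods the same is a kappa value with no statement of uncertainty. A trial of this size can observe a very high kappa when the true agreement is clearly lower.

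At stake is the question in the title: whether HyCoSy can replace HSG as the confirmatory test after sterilization.

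**Working it through.** **Superiority.** No arithmetic is needed. Kappa has a maximum of 1, reached when HyCoSy and HSG give identical results. An independent reference would be needed to go further. The Background names laparoscopy with dye as the gold standard for tubal evaluation, but Statistics does not use it. Further Testing describes later work-up only when patency is suspected, under standard of care. Verification would therefore be partial, and no analysis of it is stated.

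**The stated 36.** It cannot be reproduced from the document, because alpha, power and prevalence are absent. With alpha 5%, one- or two-sided, and power 80 to 95%, one-sample kappa formulas give at least 77 evaluable units in every variant tried. The only method that comes close is Fisher's z for two independent correlations: 2 × ((1.96 + 0.84)/(2.647 − 1.832))² + 3 ≈ 27 per group, and 27/0.8 gives 34. At one-sided 5% and 90% power it gives 29 per group, or 37 after inflation. That method does not fit one kappa from paired categorical readings.

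**Inputs for the check.**
- Units: 36 women, or 36 × 0.8 = 28.8, about 29 evaluable; at most 72 or 58 tubes, here treated as independent.
- Threshold: kappa 0.95, from Statistics.
- Assumed: one-sided 5%; equal marginals; patency π of 50% (the most favourable to the plan for the bounds below) and 10%. The documents give no patency prevalence.

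**Formulas.** At kappa k the discordance probability is (1 − k) × 2π(1 − π). At k = 0.95 this is 0.05 × 0.5 = 0.025 for π = 50%, and 0.05 × 0.18 = 0.009 for π = 10%. The chance of no discordance in n units is 0.975ⁿ or 0.991ⁿ. With no discordance observed, the exact one-sided 95% upper limit for discordance is 1 − 0.05^(1/n). Dividing by 2π(1 − π) and subtracting from 1 gives a lower bound for kappa, approximate because chance agreement is held fixed.

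| | 29 women | 36 women | 58 tubes | 72 tubes |
|---|---|---|---|---|
| P(no discordance), true kappa 0.95, π 50% | 0.480 | 0.402 | 0.230 | 0.162 |
| Same, π 10% | 0.769 | 0.722 | 0.592 | 0.522 |
| Lower bound at no discordance, π 50% | 0.804 | 0.840 | 0.899 | 0.918 |
| Same, π 10% | 0.455 | 0.556 | 0.720 | 0.774 |

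The first two rows need no choice of interval. Any rule that takes perfect agreement as proof of kappa above 0.95 errs at least 16% of the time at a true 0.95, against the 5% allowed. The exact-based bound first exceeds 0.95, with no discordance, at 119 independent units (π 50%) or 332 (π 10%).

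**Two readings of Statistics.**
- As an exact one-sided 5% test of 0.95 against 0.99: the smallest attainable p-value with women as units is the first row, 0.480 or 0.402. There is no rejection region.
- As a point rule (observed kappa at least 0.95), by exact multinomial enumeration for 29/36 women: a true kappa of 0.90 passes 23%/16% of the time at π 50% and 56%/50% at π 10%. A true 0.95 passes 48%/40% and 73%/70%.

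**Inconclusive readings.** In 36 women with an even split and otherwise perfect agreement, one inconclusive HyCoSy gives observed agreement 35/36 = 0.972 and chance agreement (18 × 17 + 18 × 18)/36² = 0.486. Kappa is (0.972 − 0.486)/(1 − 0.486) = 0.946, already below 0.95. Statistics names the category but does not say how it is scored.

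**The case against.** The primary objective in Objectives is equivalence only, and Statistics names agreement as its outcome. The Background ties superiority to other endpoints: "possible overall superiority of HyCoSy to HSG from a time effective and pain scale model". That is fair. A reader might infer that a misleading superiority analysis of patency is planned; none is. What stands is a mismatch: three statements of purpose include superiority on patency, and no analysis can address it.

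The 95% sentence is worded as an assumption following a detection claim, so it may not be a decision rule. The point-rule figures therefore apply only under that reading. The test reading fails as well, and no third criterion is given.

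Other intervals look better. At 50% patency with no discordance, a profile-likelihood bound is 0.954/0.963 for 58/72 independent tubes, but it would claim kappa above 0.95 at a true 0.95 in 22%/16% of trials. The large-sample bound equals 1.00 at perfect agreement, which is an artefact. Neither rescues the claim at one-sided 5%.

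Two stronger inferences should be resisted. One is that passing about half the time at a true 0.95 is itself a flaw: a point threshold commonly behaves so when the truth sits on it, and at 10% patency the rate is 73%/70%. The other is that pairing of tubes simply moves per-tube results toward the per-woman ones. If the second tube copies the first with probability 0.5, at kappa 0.90 and 50% patency, the point rule passes 27%/18% (29/36 women), above both independent tubes (21%/12%) and women (23%/16%).

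**Conclusion.** Wrong as written, and to be corrected before analysis. Part (a) follows from the text alone. Part (b) holds under both readings of Statistics, at both patency levels, and for women or independent tubes: perfect agreement cannot establish kappa above 0.95 at one-sided 5%. The sizes rest on assumed alpha, patency and equal marginals. High placement success (about 96.5% bilateral, in Objectives) suggests that patency is uncommon, which lowers the bounds further, but placement is not occlusion and the document gives no patency rate. None of this says that HyCoSy agrees poorly with HSG. The design can estimate agreement; it cannot certify sameness or superiority on patency.

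**What to change.** 1. In the Hypothesis, the primary objective, Aim 1 and the Background objective, replace the equivalence and superiority wording for patency with estimating agreement with HSG. Removing superiority alone would leave equivalence claims that Statistics could not support. Pain and time comparisons stay secondary.

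2. In Statistics, delete the 95% versus 99% detection claim and the sameness sentence, and state: *Kappa, raw agreement, and agreement specific to patent and occluded results will be reported with 95% confidence intervals by a method valid at or near perfect agreement, not the large-sample standard error. The methods will not be declared the same on a point kappa. With 29 to 36 women the trial cannot establish kappa above 0.95.*

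3. Make the woman the unit for the primary interval, for example both tubes occluded or not. A usable method is the exact-binomial limit on discordances divided by (1 − chance agreement), which is approximate for kappa. Its one-sided 95% version covered 97 to 100% with independent units in the settings checked. Per-tube results need an interval that allows for pairing within women: with fully paired tubes (36 women, kappa 0.90, 50% patency) the independent-unit interval covered only 84% in simulation.

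4. Count an inconclusive HyCoSy as non-agreement in the primary analysis, with a sensitivity analysis excluding it. If all results fall in one category, report kappa as not estimable.

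The cost is wording and an interval calculation, with no extra patients or procedures. The downside is a more modest conclusion.

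### The 36 planned women (about 29 evaluable) cannot detect kappa 0.95 against 0.99: under favourable assumptions for a one-sided 5% test, best-possible power is about 28% to 32%, or 9% to 10% in the direction a claim of sameness needs

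*Combined protocol and SAP*

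**What the plan says.** Under Experimental Design, "Thirty-six women who are undergoing post-Essure tubal occlusion evaluation will be invited to participate in this study". Each woman has both tests. Under Statistics, the primary outcome is agreement between HSG and HyCoSy on tubal patency, measured by kappa. HSG is binary and serves as the reference, while "the air-bubble HyCoSy will indicate either patency, non-patency, or inconclusive".

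The sample-size statement is "To detect a difference in kappa (a correlation) as small as 95% vs 99% you will need 36 with a 20% non-compliance rate". The next sentence extends it: "This means that you will be able to detect a difference as small as 95-99 OR anything larger". The conclusion drawn is "This translates into the assumption that even a 95% kappa is acceptable enough to call the methods" the same.

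No alpha, sidedness, power, null value, patency rate, unit (woman or tube) or formula is given. This is the only sample-size justification. It also supplies the only criterion behind the stated objective ("our primary objective is to determine if HyCoSy with air bubbles is equivalent to HSG in the diagnosis of tubal patency"), the primary aim ("To demonstrate an equivalent or superior evaluation of fallopian patency by HyCoSy using air-bubbles in comparison to HSG") and the Background wording ("is equivalent or superior to HSG in evaluation of fallopian tube occlusion").

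**The concern.** Kappa 0.95 and kappa 0.99 both mean almost no disagreement. With about 29 pairs of results, either value usually produces none or one discordant pair, so the data can hardly tell them apart. A statement that the trial can detect this gap, or anything larger, looks untrue on its face.

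The stake is how the result will be read. The title asks whether HyCoSy can replace HSG as the confirmatory test after sterilisation. A reader relying on the Statistics section could take a kappa of 0.95 or more as powered evidence that the tests are interchangeable, when it may be a chance result.

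**Working it through.** **Inputs from the plan.** Kappa values 0.95 and 0.99 (Statistics); 36 women (Experimental Design and Statistics); 20% non-compliance (Statistics), so 36 × 0.8 = 28.8, about 29 evaluable.

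**Assumptions, because the plan is silent.** One-sided 5% test; both tests call the same proportion p patent (equal margins); p = 0.5, the favourable case, with 0.1 as a contrast; one binary result per woman, with tubes as a sensitivity check.

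**1. Trying to reproduce 36.** The goodness-of-fit formula for a 2×2 kappa, with null 0.99, one-sided 5%, 80% power and p = 0.5, has effect size 0.02²/0.005 + 2 × 0.01²/0.4975 = 0.0804. Then n = (1.645 + 0.842)²/0.0804, or 77 evaluable. This is the smallest of the kappa-based results tried. Two-sided, the formula gives 98 (null 0.99) or 479 (null 0.95). The large-sample standard-error formula gives 182 or 334. None gives about 29 evaluable or 36 in total.

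**2. Disagreement rates.** P(disagree) = 2p(1 − p)(1 − κ). At p = 0.5 this is 0.5 × 0.01 = 0.005 for κ = 0.99 and 0.5 × 0.05 = 0.025 for κ = 0.95. Among 29 women the expected number of disagreements is 29 × 0.005 = 0.15 against 29 × 0.025 = 0.73.

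**3. Best possible power, null 0.99 and truth 0.95.** The most powerful test rejects for many disagreements and randomises at the boundary to use the full 5%.
- n = 29: rejecting at 2 or more has size 0.0093 and power 0.163. Exactly one disagreement has probability 0.126 under the null and 0.357 under the alternative. Power = 0.163 + [(0.05 − 0.0093)/0.126] × 0.357 = 0.279.
- n = 36: the same steps give 0.227 + [(0.05 − 0.0141)/0.151] × 0.371 = 0.315.

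A usable test without randomisation has 16% and 23%. At p = 0.1 the ceiling is about 23% for both sizes.

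**4. Best possible power, null 0.95 and truth 0.99.** This is the direction that a claim of sameness needs. Even zero disagreements is too likely under the null (0.975^29 = 0.480; 0.975^36 = 0.402) to reject at 5%, so a non-randomised test has no power. The randomised ceiling is 0.05 × 0.995^n/0.975^n:
- n = 29: 0.05 × 0.865/0.480 = 0.090.
- n = 36: 0.05 × 0.835/0.402 = 0.104.

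Perfect agreement first rejects 0.95 when 0.975^n ≤ 0.05, which is n = 119.

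**5. Tubes as independent units.** With 29 × 2 = 58 or 36 × 2 = 72 tubes and null 0.99, the ceiling is 45% or 54%. With null 0.95 it is 0.05 × 0.748/0.230 = 16% or 0.05 × 0.697/0.162 = 22%.

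**6. Size needed.** At p = 0.5 and one-sided 5%, the exact disagreement-count test holds 80% power from 220 evaluable results with null 0.99 (rejecting at 4 or more), and from 250 with null 0.95. At p = 0.1 and null 0.99 it needs 612.

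**7. Resolution of the 0.95 benchmark, one result per woman.** With one disagreement, kappa is largest when the calls are balanced.
- n = 36: observed agreement 35/36 = 0.9722, chance agreement (19 × 18 + 17 × 18)/36² = 0.5, so κ = 0.4722/0.5 = 0.944.
- n = 29: observed agreement 28/29 = 0.9655, chance agreement 420/841 = 0.4994, so κ = 0.931.

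If the one disagreement is an inconclusive HyCoSy, the caps are 0.946 and 0.933. An unrounded 0.95 is therefore met only by perfect agreement. At p = 0.5 that occurs in 48% (29) or 40% (36) of trials if true kappa is 0.95, and in 86% or 83% if it is 0.99.

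**The case against.** The strongest reply is that the plan omits the inputs, so any power figure is the reviewer's construction. That stands as a limit on the numbers. A reader might take 28% and 32% as absolute ceilings, and the documents do not support that. If all disagreements run one way, the figures are 29% and 33%; at one-sided 10% they are 42% and 44%. Large-sample approximations give nominal power of up to about 51%. Rejecting on any single disagreement gives 52% or 60%, but its true type I error is 13.5% or 16.5%. None of these choices reaches 80%.

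A second reply is that the natural unit may be the tube, since Appendix A records tube findings. This has force against step 7. A reader might infer that 0.95 can never be met without perfect agreement, but per tube one disagreement still allows kappa up to 0.966 (58 tubes) or 0.972 (72). That argument is confined to one result per woman. The power conclusion survives, even with the generous assumption that a woman's two tubes are independent.

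A reader might also infer that 36 came from a Pearson-correlation formula, because the text glosses kappa as a correlation. Fisher's z with two-sided 5% and 80% power gives 15, and 2 × 15 × 1.2 = 36. The documents do not confirm this, and it needs inputs that they do not state. Such a formula would not apply to categorical results from one paired cohort.

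Finally, whether to pursue equivalence with a larger trial or a wider margin is the sponsor's decision. The finding does not show that 36 women are too few to estimate agreement.

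**Conclusion.** The detection claim is wrong as written, and nothing elsewhere in the document rescues it. For a valid one-sided 5% test with equal margins, 50% patency and one result per woman, the best possible power is about 28% (29 women) or 32% (36) against a null of 0.99, and about 9% or 10% against a null of 0.95. The plan gives no patency rate. The 96.5% bilateral placement rate quoted under Objectives is not one, though it suggests that patency may be uncommon, which would lower these figures. The exact percentages depend on the assumptions. The conclusion does not: no kappa-based variant examined at the 5% level reaches 80% power with 29 or 36 results, or in the exact calculations with 58 or 72 independent tubes. An observed kappa of 0.95 or more would therefore describe agreement in this sample. It would not be a powered demonstration of sameness or equivalence.

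**What to change.** Keep 36 women. In the Statistics section:

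- Delete the gloss of kappa as a correlation, the 95% against 99% detection claim, and the sentence extending it to larger differences.
- State that the trial is not powered to separate kappa 0.95 from 0.99. Add that an observed kappa of 0.95 or more is descriptive and does not demonstrate that the methods are the same or equivalent, so the primary result is an estimate of agreement.
- Report kappa with an interval that does not collapse at perfect agreement. It must fit the table and unit chosen. The goodness-of-fit interval applies only if HyCoSy is reduced to two categories, and a per-tube analysis must allow for clustering within women.
- Report raw agreement with an exact bound. If all women agree, the one-sided 95% lower limit is 0.05^(1/29) = 90.2% for 29 women or 0.05^(1/36) = 92.0% for 36.
- Do not quote a standard deviation of kappa as the precision. With true kappa 0.95 and 50% patency, 40% to 48% of trials would sit at exactly 1.0, so it describes the uncertainty poorly.

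The cost is wording and one named interval method, with no extra patients, procedures or data. The downside is that the stated property becomes less favourable and the 95% rule is no longer a powered criterion.

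### The planning kappas of 0.95 and 0.99 have no stated source or patency rate, sit above what the protocol's only cited HyCoSy-versus-HSG rates imply, and cannot be told apart with about 29 women

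*Combined protocol and SAP*

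**What the plan says.** The primary outcome is agreement between air-bubble HyCoSy and HSG, with HSG as the reference: "Agreement between the evaluations will be measured using the kappa (κ) statistic". HSG is read as patent or non-patent. HyCoSy has a third category, inconclusive, and the plan does not say how kappa will treat it.

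The size is justified by a difference in kappa "as small as 95% vs 99% you will need 36 with a 20% non-compliance rate". The section adds that "even a 95% kappa is acceptable enough to call the methods" the same. It states no source for 0.95 or 0.99, no expected patency rate, no alpha or power, and no unit (woman or tube). It also does not say whether 0.95 applies to the estimate or to a confidence limit.

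Background and Significance gives one pair of HyCoSy-versus-HSG agreement figures, from post-Essure studies with Definity microspheres. They "demonstrated 100% agreement with HSG in assessing tubal patency" "and 82% agreement with respect to tubal occlusion". On air contrast the section says: "Positive and negative predictive values for air contrast HyCoSy appears to be similar to other contrast materials". It also says that studies comparing the trial's saline-air device with HSG are lacking.

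**The concern.** A planning value should be traceable to evidence or defended as a target, and 0.95 and 0.99 are neither. The nearest evidence in the protocol points well below them. Kappa also depends strongly on how many women are patent on HSG, so a planning kappa without a patency rate is not fully specified.

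The primary aim is at stake. If the cited rates apply to this device, the trial will almost certainly fail its own acceptance rule, and 36 women will have been justified by a scenario that the Background does not support. Even if they do not apply, a reader is told that the trial can distinguish 0.95 from 0.99, and at this size it cannot.

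**Working it through.** **The plan's own figure.** 36 × 0.8 = 28.8, so about 29 evaluable women. With no alpha, power, patency rate or formula stated, 36 cannot be properly reproduced. The nearest match treats the two kappas as Pearson correlations in two independent groups (Fisher z, difference 0.815). That gives 27 per group (two-sided 5%, 80% power; 34 after 20% loss) or 29 per group (one-sided 5%, 90% power; 37 after loss). This trial is not that design: each woman has both tests and there is one kappa.

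**Kappa implied by the cited rates.** Inputs: 100% agreement in HSG-patent women and 82% in HSG-occluded women (Background). HSG patency *p* is an assumption and is varied, with *q* = 1 − *p*. Observed disagreement is 0.18*q*, and chance disagreement is *q*(1.82*p* + 0.18*q*). Hence

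kappa = 1 − 0.18 / (1.82*p* + 0.18*q*).

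| HSG patency | 1.82*p* + 0.18*q* | kappa |
|---|---|---|
| 5% | 0.262 | 0.31 |
| 10% | 0.344 | 0.48 |
| 20% | 0.508 | 0.65 |
| 50% | 1.000 | 0.82 |
| limit as *p* → 1 | 1.820 | 0.901 |

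Reading the two rates as predictive values gives the same ceiling. If the other 18% are inconclusive and kept as a third level, the ceiling is 0.91. If they are dropped, the ceiling no longer applies. With 100% agreement in patent women, a kappa of 0.95 at 10% patency needs 99.0% agreement in occluded women.

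**What one disagreement does, whatever the true rates.** Count per woman and place the disagreement as favourably as possible.

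- 36 women, near-even split: kappa = 1 − (1/36)/0.5 = 0.944.
- 29 women, 14 agreed patent, 14 agreed occluded, 1 discordant: chance agreement = (15×14 + 14×15)/841 = 420/841, so kappa = 1 − (1/29)/(421/841) = 1 − 29/421 = 0.931.
- 29 women, 3 HSG-patent, one occluded woman called patent: chance agreement = (3×4 + 26×25)/841 = 662/841, so kappa = 1 − 29/179 = 0.84.

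One inconclusive result kept as a third level gives at most 0.933 (29 women) or 0.946 (36). An observed kappa is therefore either 1 or below 0.95, and no observable value lies between 0.95 and 0.99. Even true agreement of 98% gives no disagreements in 29 women only 0.98^29 = 56% of the time.

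**Chance of observing 0.95 or more under the cited rates.** This is essentially the chance of no disagreements, (*p* + 0.82*q*)^n:

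| HSG patency | 29 women | 36 women |
|---|---|---|
| 5% | 0.829^29 = 0.4% | 0.1% |
| 10% | 0.838^29 = 0.6% | 0.2% |
| 20% | 0.856^29 = 1.1% | 0.4% |
| 50% | 0.910^29 = 6.5% | 3.4% |

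Simulation with 400,000 runs agrees closely. The small shortfall comes from samples with no HSG-patent woman, where kappa can be undefined.

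**The case against.** The strongest reply is that the 100%/82% pair is for Definity, cited without a denominator or interval, while the trial uses a saline-air device for which the protocol itself says HSG comparisons are lacking. The link to air is one sentence about similar predictive values. The remark that air bubbles fade quickly belongs to hand-prepared syringes, whereas the trial device is described as giving a controlled, continuous stream. This stands, and it makes the 0.90 ceiling conditional. A reader might infer that 0.95 is out of reach whatever the sample size; the documents do not establish that, because the true kappa for this device is unknown. But missing device data is a reason to justify the planning values, not to leave them without a source.

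A second reply is that an acceptance threshold is not a forecast. A test that disagrees with HSG in 18% of occluded women should fail a rule for being the same. This also stands. A reader might infer that the rule cannot separate a good HyCoSy from a poor one, and that does not follow.

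A reader might also try to cap agreement from the Echovist figures, "83% agreement with HyCoSy compared to laparoscopy, compared to a 76% agreement with HSG and laparoscopy". That needs both figures to come from the same women, which the protocol does not say, and the reference there is laparoscopy. Nothing here rests on it.

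The single-disagreement result assumes that the woman is the unit. With 58 tubes (2 × 29), evenly split, one disagreement gives 1 − (1/58)/0.5 = 0.966, which would pass. Even so, an even split is unlikely after sterilization.

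**Conclusion.** The planning values are unsupported, and the claim to detect 0.95 versus 0.99 does not hold at this size. Two results differ in strength.

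- **Conditional.** If the Definity rates carry over to air contrast and inconclusive results are not dropped, expected kappa is at most 0.90, and about 0.31 to 0.65 at an assumed 5% to 20% patency. The rule would then be met with a chance of about 0.4% to 1.1% with 29 women (about 7% at 50% patency).
- **Free of that assumption.** Counted per woman and applied to the point estimate, 0.95 means zero disagreements among 29 or 36 women.

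The documents give no patency rate, so 5% to 20% is an assumed range. The ceiling of 0.90 does not depend on it.

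**What to change.** In the Statistics section, before any data are seen:

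1. Replace the claim of detecting 95% versus 99% with planning values that name their source and an assumed HSG patency rate, and show the kappa they imply over a range of patency.
2. State the precision that about 29 evaluable women deliver. For example, at about 7% patency some 27 are HSG-occluded (29 × 0.93 = 26.97). Agreement in 22 of 27 (81%) has an exact 95% interval of 62% to 94%. With only the remaining 2 women HSG-patent, agreement in both has an exact lower limit of 0.025^(1/2) = 16%.
3. Report agreement in HSG-occluded and HSG-patent women with exact confidence limits alongside kappa. Count inconclusive results as non-agreement, and state whether the unit is the woman or the tube.
4. Either justify 0.95 as a deliberate demand for essentially perfect agreement, or replace it with pre-set acceptance limits on the two rates. It should not simply be deleted, because it is the plan's only acceptance rule.

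This is a rewrite of one section, with no added patients or procedures. The cost is to the claim: this size can estimate agreement but gives little support for equivalence, so the stated objective becomes less ambitious.
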